1.14. Study Rationale

This study is a two-part, open-label, randomized Phase II/III study of dinutuximab and irinotecan versus irinotecan alone in subjects with relapsed or refractory SCLC. SCLC was selected based on the scientific evidence for GD2 as a therapeutic target^{24,59-61} and the profound unmet need that patients with this disease have for effective therapy.^{9,11,15} Dinutuximab will be evaluated without

IL-2 or GM-CSF due to lack of persuasive evidence that these agents are needed^{52,63} and the associated risks of added toxicity,⁴⁴ particularly in an adult population. Dosing for dinutuximab will be individualized given that pain, the most common toxicity of dinutuximab, is highly subjective and variable from patient to patient.

Part 1 of the study is designed to assess the safety, tolerability and PK of dinutuximab when administered in combination with irinotecan and to confirm the starting dose of dinutuximab for Part 2. The Part 1 starting dose of 10 mg/m²/day was selected based on prior studies of dinutuximab suggesting that doses as low as 5.25 mg/m²/day have antitumor activity,⁴⁶ and in children, little to no pain was reported with doses up to 14 mg/m²/day.⁴³ The maximum dose of 17.5 mg/m²/day was selected based on the approved daily dose of dinutuximab in children with high-risk neuroblastoma. The irinotecan dose of 350 mg/m² is consistent with the dose evaluated in second-line SCLC and the approved dose of irinotecan as monotherapy for CRC given on an every 3-week basis. Administering dinutuximab on the same schedule as irinotecan is intended to minimize subject burden.

After approximately 10 subjects in Part 1 have completed three 21-day cycles of therapy, Part 2 of the study commences with approval of the safety review committee (SRC) ([Section 12.7](#)). Part 2 of the study is designed to assess the contribution of effect of dinutuximab to irinotecan, a standard of care agent for second-line treatment of SCLC. The combination group builds upon the preclinical evidence showing that anti-GD2 mAbs act synergistically with a number of chemotherapeutic agents including irinotecan.⁶² Additionally, it is supported by recent clinical evidence showing promising activity of irinotecan and dinutuximab in children with neuroblastoma,⁶³ and in the setting of SCLC, evidence suggesting that irinotecan in combination may be more effective than single-agent therapy.²² The topotecan group is included given it is the only currently approved agent for second-line treatment of (relapsed-sensitive) SCLC. The dose and schedule for topotecan (1.5 mg/m² for 5 consecutive days of every 21-day cycle) is the approved dose and schedule for SCLC. Evaluation of the effect of the combination group against the topotecan alone group is relegated to a secondary objective. Owing to the poor prognosis of patients with relapsed and refractory SCLC, OS is the primary outcome measure of interest. The study findings are intended to support registration of dinutuximab (in combination with irinotecan) if warranted.

1.15. Summary of Clinical Safety from Part 1 of the DIV-SCLC-301 Study

The SRC for the DIV-SCLC-301 study met to review the safety and tolerability data entered into the electronic data capture (EDC) system for Part 1 of the study. At the time of the data cutoff, 12 subjects with SCLC had been exposed to dinutuximab and irinotecan for a mean of 3.2 cycles (range: 2-5 cycles). The maximum dose of dinutuximab administered was 16 mg/m² and three subjects had data entered into the EDC at this dose level. The median infusion time for dinutuximab during Cycle 1 was 2 hours and 30 minutes (interquartile range [IQR]: 2 hours and 27 minutes, 3 hours and 4 minutes). The median time for subsequent infusions of dinutuximab was 1 hour and 8 minutes (IQR: 1 hour and 0 minutes, 1 hour and 30 minutes). Subjects received a mean dose of 22.8 mg of dinutuximab (range: 15-35 mg) and 649.2 mg of irinotecan (range: 420-777 mg). Dose reductions were not required for dinutuximab at any time; two subjects required a dose reduction in irinotecan. [Table 4](#) presents total drug exposure by cycle for dinutuximab and irinotecan.

Table 4: Summary of Dinutuximab and Irinotecan Exposure (Part 1)

| Cycle | Mean (Min, Max) Dinutuximab Dose (mg) | Mean (Min, Max) Irinotecan Dose (mg) | No. of Subjects (%) |
|--------------|--|---|--------------------------------|
| Cycle 1 | 19.0 (15, 22.2) | 664.8 (525, 777) | 12 (100) |
| Cycle 2 | 21.4 (15.3, 26) | 644.8 (420, 777) | 12 (100) |
| Cycle 3 | 25.9 (21, 30) | 649.6 (420, 777) | 9 (75) |
| Cycle 4 | 28.3 (24.2, 31) | 587 (420, 760) | 4 (33.3) |
| Cycle 5 | 35.04 | 760 | 1 (8.3) |

A total of 105 treatment-emergent AEs (TEAEs) were reported for the 12 subjects during Part 1 to the last data cutoff for the SRC. Diarrhea (75% of subjects), back pain (58.3%), nausea (41.7%), and vomiting (33.3%) were the most commonly reported AEs by preferred term.

Nine serious adverse events (SAEs) for five subjects were reported: hypercalcemia, community acquired pneumonia, Clostridium difficile (C. diff) colitis, peripheral arterial occlusive disease, bronchitis, acute respiratory failure, elevated creatinine, clinical deterioration and sepsis (with pancytopenia). Overall, the SAEs that were reported were representative of the background disease in this population and do not reflect a change in the safety profile of dinutuximab in SCLC patients.

Pain was reported in 8 of the 12 subjects and in 15 of 38 (39%) treatment cycles. Mild pain (Grade 1) was most often reported: Grade 1 (82.7% of pain reports), Grade 2 (3.4%) and Grade 3 (13.8%). The median duration of pain was <1 day (IQR: <1 day, <1 day) with most cases resolving within hours of completing the infusion. Opioid analgesics were administered either as premedication or as treatment for pain in 4 subjects and in a minority of treatment cycles (21% of cycles). Pain was commonly managed through conservative measures consisting of decreasing the dinutuximab infusion rate, briefly interrupting the infusion (<30 minutes) and/or administering non-steroidal anti-inflammatory drugs (NSAIDs). Reports of pain in the neck, lower and upper extremities, abdomen, back and pelvis/hip were documented in the EDC. Three subjects reported chest pain and/or pressure during the dinutuximab infusion in cycles 1, 2, 4 and 5. The chest pain/pressure was determined to be non-cardiac in etiology. Pain did not result in any treatment discontinuations and has not required long-term management.

Nine subjects experienced diarrhea. According to the Investigators' assessments, seven events of diarrhea were possibly or probably related to irinotecan, two events were possibly or probably related to irinotecan and dinutuximab, two events were not related to either drug and one event had no causality noted. Diarrhea events lasted a median of 4 days (IQR: 1.5 days, 7 days). Overall, 91.7% of diarrhea reported was graded a CTCAE Grade 1 and 8.3% was graded a CTCAE Grade 2.

The data reviewed at the time of the data cutoff did not demonstrate any safety signals or otherwise trends based upon dosing, infusion rates or number of cycles. Dose levels of 16 mg/m² were tolerated and no unanticipated AEs were reported. No suspected unexpected serious adverse reactions were reported. The SRC concluded that Part 2 of the study should open at a starting dose of dinutuximab of 14 mg/m² and no safety modifications to the protocol were required for Part 2.

The SRC reviewed additional data via a subsequent ad hoc meeting; at that time, 8 of the 12 subjects in Part 1 had received a dose of 16 mg/m²/day or higher. The data at higher doses showed comparable safety and tolerability to the data at lower doses (data on file), and thus the SRC recommended increasing the starting dose of dinutuximab for Part 2 to 16 mg/m²/day.

2. STUDY OBJECTIVES

2.1. Primary Objective

The primary objective of this study is to compare OS in subjects treated with dinutuximab and irinotecan versus subjects treated with irinotecan alone as a second-line treatment for relapsed or refractory SCLC.

2.2. Secondary Objectives

The secondary objectives of the study are:

- To compare progression-free survival (PFS), objective response rate (ORR) (complete response [CR] + partial response [PR]) and clinical benefit rate (CR + PR + stable disease [SD]) in subjects treated with dinutuximab and irinotecan versus subjects treated with irinotecan alone.
- To compare the safety of subjects treated with dinutuximab and irinotecan versus subjects treated with irinotecan alone.
- To evaluate the pharmacokinetics of subjects treated with dinutuximab.
- To compare OS, PFS, ORR, and clinical benefit rate (CBR) in subjects treated with dinutuximab and irinotecan versus subjects treated with topotecan alone.

2.3. Exploratory Objectives

The exploratory objective of the study is to assess the relationship between selected biomarkers and survival of subjects treated with dinutuximab.

3. ELIGIBILITY CRITERIA

3.1. Inclusion Criteria

Subjects must meet all of the following criteria:

- 3.1.1. Provide a signed informed consent form before any screening procedures.
- 3.1.2. Aged ≥ 18 years on the date of signing the informed consent form.
- 3.1.3. Have histologically or cytologically confirmed SCLC (undifferentiated small cell carcinoma arising in or consistent with lung cancer origin).
- 3.1.4. Documented (radiographic evidence of) relapse or disease progression during or after first-line platinum-based therapy (subjects refractory to initial platinum-based therapy are eligible).
- 3.1.5. No more than 1 prior regimen for SCLC. First-line platinum-based therapy followed by maintenance therapy is considered a single regimen provided there is no intervening disease progression.
- 3.1.6. Have no curative therapy available.
- 3.1.7. Have a life expectancy of at least 12 weeks.
- 3.1.8. Have Eastern Cooperative Oncology Group (ECOG) performance status of 0 or 1.
- 3.1.9. Have adequate bone marrow function as assessed by the following laboratory test results:
 - Hemoglobin ≥ 9.0 g/dL or ≥ 5.6 mmol/L (erythropoietin or transfusion permitted).
 - Absolute neutrophil count (ANC) $\geq 1,500/\text{mm}^3$ or $\geq 1.5 \times 10^9/\text{L}$ (growth factors permitted).
 - Platelet count $\geq 100,000/\text{mm}^3$ or $\geq 100 \times 10^9/\text{L}$ (transfusions or thrombopoietic growth factors permitted).
- 3.1.10. Have calculated creatinine clearance (CrCL) ≥ 30 mL/minute (using Cockcroft and Gault's formula) or serum creatinine ≤ 1.5 times below the ULN.
- 3.1.11. Have adequate hepatic function, as assessed by the following laboratory test results:
 - Total bilirubin ≤ 1.5 times the ULN. (Subjects with Gilbert's Syndrome or other benign congenital hyperbilirubinemia may be eligible at the investigator's discretion in consultation with the Medical Monitor.)

- Aspartate aminotransferase (AST) and alanine aminotransferase (ALT) ≤ 3.0 times ULN in subjects without liver metastases or ≤ 5.0 times ULN in subjects with liver metastases.

3.1.12. Women of reproductive potential must have a negative urine or serum beta human chorionic gonadotropin (β -HCG) pregnancy test obtained within 7 days prior to the first dose of study treatment (dinutuximab and/or chemotherapy)

- Women not of reproductive potential are female subjects who are postmenopausal or permanently sterilized (e.g. tubal occlusion, hysterectomy, bilateral salpingectomy).

3.1.13. Women of reproductive potential must agree to consistently use one form of highly effective contraception plus one additional form of contraception simultaneously or to practice complete abstinence from vaginal intercourse. The requirement for two forms of contraception or complete abstinence from vaginal intercourse applies from the time of informed consent until 90 days following the last dose of all study drugs. Male subjects who are sexually active with a female of reproductive potential must agree to use a condom from the time of informed consent until 90 days following the last dose of all study drugs.

The following are examples of highly effective and additional methods of contraception:

Highly effective methods (must use one):

- Hormonal associated with inhibition of ovulation (oral, injectable, implantable, intravaginal, transdermal)
- Intrauterine device (IUD)
- Intrauterine hormone-releasing system (IUS)
- Tubal ligation
- Vasectomy for partner

Additional effective methods (must use one):

- Male or female condom with or without spermicide
- Cap, diaphragm or sponge with spermicide
- Combination of male condom with either cap, diaphragm or sponge with spermicide (double barrier methods)

3.2. Exclusion Criteria

Subjects are excluded if they meet any of the following criteria:

- 3.2.1. Candidate for re-treatment with original platinum-based regimen as second-line therapy.
- 3.2.2. Prior treatment with irinotecan, topotecan or dinutuximab.
- 3.2.3. Have active brain metastases. Subjects with brain metastases are allowed if they completed definitive brain therapy, are asymptomatic and radiologically stable, and if they are not currently receiving corticosteroids or radiation. Subjects in whom steroids are being tapered may be eligible with prior approval of the Medical Monitor.
- 3.2.4. Have mixed small-cell and non-small-cell histologic features.
- 3.2.5. Have a previous or concurrent cancer that is distinct in primary site or histology from the cancer being evaluated in this study, except cervical carcinoma in situ, treated basal cell carcinoma, superficial bladder tumors (Ta and Tis [carcinoma in situ]) or any previous cancer curatively treated <3 years ago.
- 3.2.6. Have a history or current evidence of uncontrolled cardiovascular disease including but not limited to the following conditions:
 - Congestive heart failure of New York Heart Association (NYHA) grade 3 or greater.
 - Unstable angina (symptoms of angina at rest) or new-onset angina within 6 months.
 - Arterial thrombosis, deep vein thrombosis, or pulmonary embolism within 6 months.
 - Myocardial infarction or stroke within 6 months.
 - Pericarditis (any CTCAE v.4.03 grade), pericardial effusion (CTCAE v4.03 Grade ≥ 2).
- 3.2.7. Have a history of atypical thrombotic thrombocytopenic purpura (TTP) or hemolytic uremic syndrome (HUS).
- 3.2.8. Women who are pregnant or breast-feeding.
- 3.2.9. Have not recovered from prior surgery, significant trauma, systemic anticancer therapy (e.g., chemotherapy, biologic therapy, immunotherapy), radiation therapy or investigational therapy to Grade 1 or better toxicity prior to enrollment (Part 1) or randomization (Part 2).
- 3.2.10. Have had organ allograft or hematopoietic transplantation.

3.2.11. Known to be human immunodeficiency virus (HIV) positive.

3.2.12. Have an active infection requiring treatment or one that is clinically serious in the Investigator's opinion.

3.2.13. Have received a live vaccine within 6 months of enrollment (Part 1) or randomization (Part 2).

3.2.14. Exposure to strong CYP3A4 and/or UGT1A1 inhibitors and strong CYP3A4 inducers within 14 days of enrollment (Part 1) or randomization (Part 2).

3.2.15. Have any clinical condition that is considered unstable or might jeopardize the safety of the subject and / or influence the subject's compliance in the study.

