|--|---|

| | |
|--|---|
| | 
 • Have active brain metastases. Subjects with brain metastases are allowed if they completed definitive brain therapy, are asymptomatic and radiologically stable, and if they are not currently receiving corticosteroids or radiation. Subjects in whom steroids are being tapered may be eligible with prior approval of the Medical Monitor. • Have mixed small-cell and non-small cell histologic features. • Have a previous or concurrent cancer that is distinct in primary site or histology from the cancer being evaluated in this study, except cervical carcinoma in situ, treated basal cell carcinoma, superficial bladder tumors (Ta and Tis [carcinoma in situ]) or any previous cancer curatively treated <3 years ago. • Have a history or current evidence of uncontrolled cardiovascular disease including but not limited to the following conditions: 
 – Congestive heart failure of New York Heart Association (NYHA) grade 3 or greater. – Unstable angina (symptoms of angina at rest) or new-onset angina within 6 months. – Arterial thrombosis, deep vein thrombosis, or pulmonary embolism within 6 months. – Myocardial infarction or stroke within 6 months. – Pericarditis (any CTCAE v4.03 grade), pericardial effusion (CTCAE v4.03 Grade ≥ 2). • Have a history of atypical thrombotic thrombocytopenic purpura (TTP) or hemolytic uremic syndrome (HUS). • Women who are pregnant or breast-feeding. • Have not recovered from prior surgery, significant trauma, systemic anticancer therapy (e.g., chemotherapy, biologic therapy, immunotherapy), radiation therapy or investigational therapy to Grade 1 or better toxicity prior to enrollment (Part 1) or randomization (Part 2). • Have had organ allograft or hematopoietic transplantation. • Known to be human immunodeficiency virus (HIV) positive. • Have an active infection requiring treatment or one that is clinically serious in the Investigator’s opinion. • Have received a live vaccine within 6 months of enrollment (Part 1) or randomization (Part 2). • Exposure to strong CYP3A4 and/or UGT1A1 inhibitors and strong CYP3A4 inducers within 14 days of enrollment (Part 1) or randomization (Part 2). • Have any clinical condition that is considered unstable or might jeopardize the safety of the subject and / or influence the subject’s compliance in the study. |

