 †Dose will be escalated if maximal pain with the prior dose is \leq Grade 1 or Grade 2/3 that in the view of the Investigator is adequately managed and the drug is otherwise tolerated up to a maximum dose of 17.5 mg/m² IV (If this dose is reached, the dose increment would be 1.5 mg/m²). Dose will be de-escalated in 2 mg/m² decrements for toxicity to as low as 8 mg/m²/cycle per Section 6.7. If the dose is reduced from 17.5 mg/m², the initial dose decrement would be 1.5 mg/m² (to 16 mg/m²).
 *2:2:1 ratio (184/Group A, 184/Group B and 92/Group C); randomization will be stratified by relapse-free interval (<3 months, \geq 3 months).
 †Treatment continues during the study until disease progression or intolerable toxicity.

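### Exclusion 3.2.5 exempts other cancers curatively treated less than 3 years ago and so bars those cured longer ago; the inequality is probably reversed

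*Protocol*

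**What the plan says.** Section 3.2 of the protocol lists criteria any one of which excludes a subject. Criterion 3.2.5 opens with "Have a previous or concurrent cancer that is distinct in primary site or histology from the cancer being evaluated in this study, except" and then gives the exceptions: in situ cervical carcinoma, treated basal cell carcinoma, and finally "superficial bladder tumors (Ta and Tis [carcinoma in situ]) or any previous cancer curatively treated <3 years ago". The exclusion list in the synopsis ends the same criterion in the same way: "or any previous cancer curatively treated <3 years ago". Neither the protocol nor the SAP states another interval or direction for previous cancers, or gives a reason for treating recent cancers more leniently than old ones.

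The criterion feeds into later steps. Protocol 5.2 plans for about 200 centers. Protocol 12.6 counts meeting the eligibility criteria among the critical requirements to be tracked by metrics. Protocol 10.5 and SAP 4.4 call for displays of randomized subjects who met an exclusion criterion, and SAP 4.5 includes eligibility in the review of protocol deviations.

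**The concern.** The last item sits inside a list of exceptions, so its effect is to let subjects in. A less-than sign there admits the recently treated cancer and leaves the one cured long ago under the general exclusion. That is the opposite of what a 3-year limit on previous cancer would ordinarily be expected to do. It also fits poorly with the other exceptions, which are in situ, superficial or treated basal cell tumors. An exemption for a cancer of any type and stage, granted because its treatment was recent, is of a different kind.

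If the sign is wrong, two things follow. Sites that apply the text literally and sites that apply the presumed intent will make opposite decisions about the same patient. The eligibility listing and deviation review would also be made against the wrong rule: an enrolled subject with a long-cured cancer would be listed as a violation, and one curatively treated recently would not.

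**Working it through.** No published figure is at issue and no formula applies. The check is to apply the text to each kind of case under the two readings that the sentence allows.

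**Reading 1 (plain):** the last item is one of the exceptions. **Reading 2:** the last item is a second, separate exclusion.

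| Case | Reading 1 | Reading 2 |
|---|---|---|
| Unlisted previous cancer, curatively treated <3 years ago | allowed | excluded |
| Unlisted previous cancer, curatively treated ≥3 years ago | excluded | excluded (opening clause) |
| Unlisted cancer, concurrent or not curatively treated | excluded | excluded |
| Named tumors (cervical in situ, basal cell, superficial bladder) | exempt at any time | exempt, yet excluded if curatively treated <3 years ago |

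Reading 2 strains the grammar. It makes the 3-year limit empty for unlisted cancers, because the opening clause already excludes them at any time, and it contradicts the exemption of the named tumors. Neither of the two readings keeps out recently treated unlisted cancers and admits long-cured ones.

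**Evidence on direction.** The other time limits in section 3.2 can be set beside this one:

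- 3.2.6, new-onset angina: 6 months
- 3.2.6, arterial thrombosis, deep vein thrombosis or pulmonary embolism: 6 months
- 3.2.6: "Myocardial infarction or stroke within 6 months"
- 3.2.13: "Have received a live vaccine within 6 months of enrollment (Part 1) or randomization (Part 2"
- 3.2.14, strong CYP3A4 or UGT1A1 inhibitors and strong CYP3A4 inducers: 14 days

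All 5 exclude the recent event; 3.2.5, read plainly, exempts it.

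**Could the sign be a rendering fault?** The printed page was not available to check. The same sign appears in both the synopsis and 3.2.5, and a less-than sign comes through as expected elsewhere, for example in the footnote to Figure 1: "randomization will be stratified by relapse-free interval (<3 months". A fault in both places is unlikely.

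**Where the criterion enters the analysis.** SAP 4.3 builds the Per Protocol population on criteria 3.1.3, 3.1.4, 3.1.5 and 3.2.2, and does not name 3.2.5. The ITT, mITT, Safety and Efficacy Evaluable definitions do not use it either. The primary OS test in SAP 4.9.1 is on the ITT set, so it keeps every randomized subject in Groups A and B however 3.2.5 is read.

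**The case against.** The strongest reply accepts the literal reading and disputes its importance.

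- **No analysis set turns on 3.2.5.** This is correct, and it sets the ceiling on the finding.
- **Only curatively treated previous cancers are exempted.** This is correct. Concurrent cancers and those not curatively treated stay excluded on any reading. Other criteria also narrow who can enter: "Have a life expectancy of at least 12 weeks" (3.1.7), "Have Eastern Cooperative Oncology Group (ECOG) performance status of 0 or 1" (3.1.8), recovery from earlier treatment to Grade 1 or better (3.2.9), and no unstable condition (3.2.15). With an assumed control median OS of 6 months, a curatively treated second cancer has little time to affect all-cause survival. These points limit the harm but do not repair the rule.
- **The evidence for reversal is circumstantial.** Three of the five look-back limits belong to one criterion, and all five are stand-alone exclusions, not exceptions within an exclusion. Section 3.2 also contains history exclusions with no time limit: 3.2.2 (prior irinotecan, topotecan or dinutuximab), 3.2.7 (thrombotic thrombocytopenic purpura or hemolytic uremic syndrome) and 3.2.10 (transplant). Barring a remote event is therefore not foreign to the list. This stands: the evidence supports reversal but does not prove it.
- **Deviations are found by clinical review, not by a mechanical check of the sign, and nothing shows that a metric encodes 3.2.5.** This is fair as far as it goes. But clinical reviewers also need to know which rule they are applying, and SAP 4.4 lists subjects by whether they met the written criterion.
- **How sites applied the rule cannot be seen from these documents.** This is true, and it is a reason to ask the sponsor.

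**Conclusion.** The concern holds. As written, 3.2.5 and the synopsis admit an unlisted cancer curatively treated less than 3 years ago and exclude one curatively treated 3 or more years ago, and no other text corrects this. Confidence in that reading is high. That the sign is reversed is the likelier explanation, but it remains an inference that only the sponsor can settle.

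The number of subjects affected cannot be computed from the documents. The statistical consequence is limited: eligibility is fixed before randomization, so any effect on the Group B versus Group A comparison of OS is non-differential and probably very small. Power, alpha and the event target are untouched. The consequence lies in the enrolled population and in the accuracy of the eligibility listing. It is worth correcting because this is an operative entry rule.

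**What to change.** The sponsor should state the intended direction of the 3-year limit and amend 3.2.5 and the synopsis together so that the exception does what is meant. If the literal rule is intended, one sentence giving the reason would settle the matter. Any eligibility checklist, and the eligibility metrics under Protocol 12.6, should then be aligned with the confirmed wording.

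For subjects already enrolled, use the by-subject medical history listing in SAP 4.6.1, with source records where needed, to identify those whose eligibility depends on this item. The listing in SAP 4.4 and the deviation review in SAP 4.5 can then be made against the confirmed rule before database lock. The source-record check need cover only subjects with a recorded previous cancer.

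The cost is a short amendment in two places, IRB/IEC approval before implementation (Protocol 12.1.5), and notice to about 200 centers. If the direction changes, eligibility changes for some subjects with an earlier cancer; the documents do not allow a count. Sample size, tests and endpoints stay as they are.
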